Once consent procedures are complete, caregivers receive a Qualtrics link with their initial questionnaire. Identical Qualtrics questionnaires will be sent via email to caregivers in both research conditions at baseline, 3 months, and 6 months. The three sets of questionnaires will be identical, except the baseline questionnaire will also include a contact information form and "Information about person receiving care."

Randomization:

Sixty caregivers will be randomly assigned to the "active in-home technology" condition of the system and the remaining 60 caregivers will be assigned to the "control" condition. Randomization of participants in each group will be determined by People Power employees after the consent process.

Outcome Measures:

All caregivers—regardless of randomized study condition—complete questionnaires on three separate occasions during this study: baseline, 3-months, 6-months. The four outcome measures are: (a) Zarit Burden Interview-Short Form, a questionnaire measuring caregiver burden (Zarit, Reever, & Bach-Peterson, 1980). 12 items are rated on 0-4 scale. Range: 0-48. No subscales. Higher scores represent worse outcomes; (b) Center for Epidemiological Studies Depression Scale (CES-D), a questionnaire measuring depression (Radloff, 1977). 20 items are rated on a 0-3 scale and summed (range = 0-60). There are no subscales. Higher scores represent worse outcomes. The clinical cut-off is usually set at a score of 16; (c) Beck Anxiety Inventory (BAI), a questionnaire measuring anxiety (Beck, Epstein, Brown, & Steer, 1988). 20 items are rated on a 0-3 scale and summed (range= 0-60). Higher scores indicate worse outcomes. There are no subscales. A score greater than 36 is considered to be clinically significant; and (d) Satisfaction with Life Scale, a questionnaire measuring overall life satisfaction and well-being (Diener, Emmons, Larsen, & Griffin, 1985). 5 items scored on a 1-7 scale and summed (Range = 5-35). Lower scores indicate worse outcomes. A score of 20 is considered neutral with higher scores considered increasingly more satisfied and lower scores considered increasingly more dissatisfied.

Contact initiated by study staff

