## Statistical Analysis Plan

### Primary Outcomes

All caregivers—regardless of randomized study condition—complete questionnaires on three separate occasions during this study: baseline, 3-months, 6-months. The four outcome measures include changes over the 6-month study period for the following scales: Zarit Burden Interview-Short Form, a questionnaire measuring caregiver burden (Zarit, Reever, & Bach-Peterson, 1980). 12 items are rated on 0-4 scale. Range: 0-48. No subscales. Higher scores represent worse outcomes; Center for Epidemiological Studies Depression Scale (CES-D), a questionnaire measuring depression (Radloff, 1977). 20 items are rated on a 0-3 scale and summed (range = 0-60). There are no subscales. Higher scores represent worse outcomes. The clinical cut-off is usually set at a score of 16; Beck Anxiety Inventory (BAI), a questionnaire measuring anxiety (Beck, Epstein, Brown, & Steer, 1988). 20 items are rated on a 0-3 scale and summed (range= 0-60). Higher scores indicate worse outcomes. There are no subscales. A score greater than 36 is considered to be clinically significant.; and Satisfaction with Life Scale, a questionnaire measuring overall life satisfaction and well-being (Diener, Emmons, Larsen, & Griffin, 1985). 5 items scored on a 1-7 scale and summed (Range = 5-35). Lower scores indicate worse outcomes. A score of 20 is considered neutral with higher scores considered increasingly more satisfied and lower scores considered increasingly more dissatisfied.

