### Statistical Methods

*Design:* Caregivers will be randomized into two groups: Active In-Home Technology System and Limited In-Home Technology System. Subjects will be randomized 1:1. Randomization of participants in each group will be determined by People Power employees. Analyses of caregiver health and well-being will use 2 X 3 (Condition [active treatment vs control] X Time [time 1 vs time 2 vs time 3]) mixed model analysis of variance. In all analyses, significant main effects and interactions will be decomposed using a priori or post hoc comparisons depending on whether they are hypothesized or not. Bonferroni corrections will be used to control for Type I error resulting from multiple comparisons. Statistical Power. Tests of hypothesized Group differences (active treatment vs control condition) for caregiver health and well-being will have .80 power to detect a medium effect size (one-tailed, alpha = .05). Using repeated measures analysis of variance, tests of the interaction of Condition (2 groups) X Time (3 assessments) will have power of .99 to detect a medium effect size (correlation between repeated measures  $r = .5$ , alpha = .05).

*Analysis:* Descriptive statistics will be used to summarize all the clinical characteristics and demographic outcomes. These will be summarized overall, by treatment group, by assessment time, and by treatment group and time. Continuous variables will be summarized using means, standard deviations, and ranges. Categorical data will be summarized by number and percent. To evaluate the treatment effects, we will use repeated measures ANOVAs. The other predictors will be treatment group, and time (baseline, 3-months, and 6-months for caregiver outcomes). To evaluate treatment effects, an interaction term between treatment group and time will be included

to examine treatment group-related differences in the assessments for each outcome. Each significant interaction will be followed up with paired t-tests to examine treatment differences at each set of time points. Although this study involves 4 outcomes, we do not plan formal multiple comparison adjustments if the results fit a coherent pattern that is consistent with the context of similar studies. In this case, each result will reinforce the other, rather than detracting from one another, as required by formal multiple comparisons adjustments such as Bonferroni.

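### The planned Condition x Time interaction leaves the baseline arm means free, which costs power against a baseline-adjusted joint test of months 3 and 6, and no active-minus-control contrast with a confidence interval is named

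*SAP*

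**What the plan says.** The Protocol (Randomization) puts sixty caregivers in the active condition, and "the remaining 60 caregivers will be assigned to the" control condition. The SAP (Statistical Methods) confirms 1:1 allocation. All caregivers complete the four scales at baseline, 3 months and 6 months.

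The SAP (Primary Outcomes) defines the outcomes loosely: "The four outcome measures include changes over the 6-month study period for the following scales". Under Statistical Methods, Analysis, the model is a repeated measures ANOVA. Its factors are given as "The other predictors will be treatment group, and time (baseline, 3-months, and 6-months for caregiver outcomes". The treatment test is the interaction: "To evaluate treatment effects, an interaction term between treatment group and time will be included". The follow-up is: "Each significant interaction will be followed up with paired t-tests to examine treatment differences at each set of time points". The Design paragraph adds a general rule that "significant main effects and interactions will be decomposed using a priori or post hoc comparisons".

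On power, the Design paragraph states that "tests of the interaction of Condition (2 groups) X Time (3 assessments) will have power of .99 to detect a medium effect size", with r = .5 between visits and alpha .05. It also states, for a one-tailed test at .05: "Tests of hypothesized Group differences (active treatment vs control condition) for caregiver health and well-being will have .80 power". In neither sentence is a medium effect given in SD units or as a named index.

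**The concern.** Group, Time and their interaction fit six free cell means, so the model estimates a baseline difference between arms that randomization makes zero in expectation. Discarding that knowledge costs precision. The loss comes from leaving the baseline means unconstrained, not from having baseline as a level of Time: a three-visit model with the arm means held equal at baseline would not suffer it.

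The second part is reporting. A paired t-test compares two visits within the same caregivers. A significant change in one arm and a non-significant change in the other is not an estimate of active minus control. The decomposition rule could admit a between-arm comparison, but the text available for review writes none down and mentions no confidence interval.

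At stake are power that N = 120 could deliver at no extra cost, and a prespecified treatment effect on each scale.

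**Working it through.** **Inputs.** From the documents: n = 60 per arm, N = 120, m = 3 visits, r = .5, alpha .05. Assumed: SD 1 at every visit, equal correlation r between visits, complete data, two-sided tests, largest arm difference 0.5 SD. The documents give no dropout rate and no source for r, so r runs from .3 to .8. Arm differences at months 0/3/6: sustained 0/.5/.5, linear 0/.25/.5, late 0/0/.5, waning 0/.5/.25.

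**1. The plan's own figure.** Read a medium effect as f = .25. Then λ = N f² m/(1 − r) = 120 × .0625 × 3/.5 = 45 on 2 and 236 df, and power is above .999. Leaving out the r term, λ = 22.5 and power is .992. The stated .99 is therefore reproduced or exceeded.

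In SD units, the interaction has λ = (n/2) Σdev²/(1 − r), where dev is each visit's arm difference minus the mean over the three visits. For a sustained difference d, Σdev² = (2/3)d², so λ = 30 × (2/3)d²/.5 = 40d². Setting 40d² = 45 gives d = 1.06 SD. For a linear effect ending at d, λ = 30d² and d = 1.22 SD. Power of exactly .99 needs 0.74 SD (sustained or late) or 0.85 SD (linear or waning).

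**2. Planned interaction at 0.5 SD, r = .5.**
- Sustained or late: Σdev² = .1667, λ = 30 × .1667/.5 = 10.0, power .81.
- Linear or waning: Σdev² = .125, λ = 30 × .125/.5 = 7.5, power .68.

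The multivariate form of the same interaction (2 and 117 df) gives .805 and .676, so the sphericity assumption does not explain the gap shown next.

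**3. Baseline-adjusted joint test.** Given baseline, months 3 and 6 have covariance S = [[1 − r², r − r²],[r − r², 1 − r²]], and λ = (n/2) d′S⁻¹d on 2 and 116 df. At r = .5, S = [[.75, .25],[.25, .75]] and S⁻¹ = [[1.5, −.5],[−.5, 1.5]].
- Sustained: 30 × .500 = 15.0, power .94.
- Linear or waning: 30 × .34375 = 10.31, power .82.
- Late: 30 × .375 = 11.25, power .85.

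**4. Over r** (power in the order sustained/linear/late/waning; the last column is the total N at which the planned interaction matches the adjusted test at 120):

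| r | Planned interaction | Adjusted joint test | Matching N |
|---|---|---|---|
| .3 | .66/.53/.66/.53 | .91/.75/.74/.75 | 221/195/144/195 |
| .5 | .81/.68/.81/.68 | .94/.82/.85/.82 | 177/162/133/162 |
| .7 | .96/.89/.96/.89 | .99/.94/.97/.94 | 148/140/126/140 |
| .8 | gain at most about 1 point | | 136/132/123/132 |

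Simulation at r = .5 (20,000 trials, interaction then adjusted) agrees: null .051 and .050; sustained .813 and .934; late .811 and .851.

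**5. Type I error without sphericity.** The SAP names no sphericity correction. With correlations .4 (baseline–3), .4 (baseline–6) and .8 (3–6), the uncorrected interaction F rejected a true null in .066 of 10,000 simulated trials and in .060 of a separate 20,000.

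**6. Month 6 alone, r = .5.** The adjusted standard error is √(.75 × 2/60) = .158 SD, against √(1 × 2/60) = .183 for a change score. A 0.5 SD difference is 3.16 standard errors, power .88. A 0.25 SD difference (waning) is 1.58, power .35. Against the joint test, month 6 alone wins for linear (.88 v .82) and late (.88 v .85) effects, and loses for sustained (.88 v .94) and waning (.35 v .82) effects.

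**7. Form of the adjustment.** One baseline slope common to both visits is not the same model as equal baseline means unless baseline correlates equally with both visits. With correlations .7 (baseline–3), .4 (baseline–6) and .6 (3–6), power for a late effect is .83 with a common slope and .87 with constrained means. A baseline-by-visit term is needed.

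**The case against.** The strongest reply is that the planned test is legitimate and that choosing a more efficient model is a preference. Much of this stands. The interaction is not biased, and under sphericity with complete data it holds its level. The gain rests on an r with no stated source: at r = .7 it is under 1 point for a late effect, and at r = .8 it is negligible for all four patterns. What does not fall away is that at the SAP's own r = .5 the gain is 4 to 14 points and needs no new data.

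On reporting, the SAP does plan means and SDs by arm and visit, so a reader could derive an unadjusted difference and interval. It also speaks of treatment differences in the follow-up sentence, so the word paired may be loose drafting. What is missing is a prespecified, adjusted between-arm estimate. Part of the SAP was not available for review, so this absence is claimed only for the text supplied.

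Two stronger readings are tempting and are not supported:
- A reader might infer that the .99 is miscalculated. It is not: it reproduces at f = .25, and the SAP never ties it to 0.5 SD. Only its meaning in SD units is unclear.
- A reader might infer that the SAP will judge treatment by the three-visit Condition main effect, which averages in a pre-treatment visit (one-tailed power .72/.51/.30 for sustained/linear/late at 0.5 SD and r = .5). But the SAP assigns treatment evaluation to the interaction and does not say which test its .80 describes, so this concern is conditional only.

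**Conclusion.** The point holds as one of efficiency and reporting, not of bias. With a largest effect of 0.5 SD, 60 per arm, complete data and equal correlations of .5, the planned interaction gives up 4 to 14 points of power. It would need about 133 (late) to 177 (sustained) caregivers to match what the adjusted joint test achieves with 120. The loss is 9 to 25 points at r = .3 and becomes small as r rises. If the effect really is f = .25, both tests have power near 1 and adjustment adds nothing useful.

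The validity of the planned F is itself conditional on sphericity, which the single r = .5 implies but the SAP neither checks nor corrects for. The lack of a named active-minus-control contrast with an interval matters whatever r turns out to be. The change should be made, but the planned analysis is not unusable without it.

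**What to change.** - For each scale, model the 3- and 6-month scores with condition, visit, condition-by-visit, baseline score and baseline-by-visit, with unstructured covariance. Alternatively, keep all three visits with unstructured covariance and constrain the arm means to be equal at baseline.
- Make the joint 2-df test of the two arm differences the treatment test. If the team prefers month 6 alone as primary, state that choice in advance with its trade-off (step 6 of the working).
- Replace the paired t-tests with the active-minus-control difference at months 3 and 6, each with a 95% CI. At r = .5 the half-width at one visit is about .31 SD.
- State in SD units the effect to which the .99 applies, restate power for the chosen test over r = .3 to .8, and say which test the .80 describes.

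The cost is SAP rewording and a less flattering power figure (.82 to .94 at 0.5 SD and r = .5). Baseline is already part of data collection, so nothing new is needed from caregivers. If the true r is high, little power is gained, but the between-arm estimate is still worth having.

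### Paired t-tests cannot examine treatment differences between two independent arms; the follow-up to a significant interaction needs between-arm contrasts in change, with confidence intervals

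*SAP*

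**What the plan says.** The SAP's Statistical Methods section sets up a parallel two-arm comparison: "Caregivers will be randomized into two groups: Active In-Home Technology System and Limited In-Home Technology System", with "Subjects will be randomized 1:1". The Protocol's Randomization section gives the size ("Sixty caregivers will be randomly assigned" to the active condition and the other 60 to control). Neither document describes matching.

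The analysis is a 2 x 3 mixed ANOVA with condition between caregivers and time within caregivers. The treatment effect is judged through the interaction: "To evaluate treatment effects, an interaction term between treatment group and time will be included". The Analysis paragraph then names the follow-up: "Each significant interaction will be followed up with paired t-tests to examine treatment differences at each set of time points".

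The Design paragraph has a more general rule, that "significant main effects and interactions will be decomposed using a priori or post hoc comparisons depending on whether they are hypothesized or not", followed by "Bonferroni corrections will be used to control for Type I error resulting from multiple comparisons". It does not state which comparisons these are. The planned descriptive summaries are means, standard deviations and ranges by arm and time.

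**The concern.** The test named does not match its stated purpose. With independent arms, the two members of a pair can only be the same caregiver at two times. The paired t-test then asks whether that arm changed, or, if the arms are pooled, whether caregivers as a whole changed. Neither is a treatment difference.

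This matters because the interaction has 2 degrees of freedom. When significant, it says only that the two profiles are not parallel. The follow-up must supply the interval over which they diverge, the direction and the size. Setting one within-arm p-value beside the other does not do so reliably. Two arms with the same true change can easily fall on opposite sides of .05, and two arms with quite different true changes can both fall below it. A real effect could be placed at the wrong assessment, or a real difference at 6 months could be read as improvement in both arms. The SAP also says it will weigh the direction and magnitude of results when judging whether they are coherent, which requires a between-arm estimate.

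**Working it through.** **1. Inputs.** From the documents: 60 per arm (Protocol, Randomization); three assessments; r = .5 between repeated measures and alpha = .05 (SAP, power statement). Assumed, because the documents give no values: SD 1 at each assessment, equal correlations, no dropout, and the mean profiles below.

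**2. The plan's own figure.** The SAP claims power of .99 for the interaction at a medium effect. Taking medium as f = 0.25 (assumed) with F on 2 and 236 df:
- lambda = f² x N x m = 0.0625 x 120 x 3 = 22.5 gives power .992.
- Dividing by (1 - r), lambda = 45 gives power above .999.

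The stated figure reproduces, and the gating test is not disputed.

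**3. What the paired test measures.** The SD of change is sqrt(2(1 - r)) = sqrt(2 x 0.5) = 1 SD. For a true within-arm change d, the paired t has noncentrality d x sqrt(60). At d = 0.25 this is 1.94, and the two-sided power is .478. If both arms truly change by 0.25 SD, so that treatment has no effect, the chance that exactly one arm is significant is 2 x .478 x .522 = .499. A between-arm test on change rejects in 5%.

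**4. Adding the interaction gate under no effect.** Simulation, 100,000 trials, both arms 0, .25, .25: the interaction is significant in 5.1%. Interaction significant together with exactly one arm significant occurs in 4.1% for either baseline comparison, and in 5.0% for any of the three time pairs. The gate therefore controls the overall false-positive rate.

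**5. A true effect at 6 months only.** Control 0, .3, .3; active 0, .3, .8. The between-arm differences are 0, 0, .5, so the interaction f is 0.118, lambda = 0.0139 x 360 / 0.5 = 10 and power is .81. Simulation gives .809. Among trials with a significant interaction:

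| Interval | True difference | Paired-test pattern | Between-arm test on change rejects |
|---|---|---|---|
| Baseline to 3 months | 0 | exactly one arm significant, 49% | 6% |
| Baseline to 6 months | 0.5 SD | both arms significant, 56% | 90% |
| 3 to 6 months | 0.5 SD | active only significant, 95% | not computed |

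The 49% divides about evenly between active-only and control-only, so the pattern there is noise.

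**6. Bonferroni.** With the six paired tests (3 time pairs x 2 arms) at .05/6 and the two between-arm tests at .05/2, the 3-month comparison is 47% against 3%. At 6 months both arms are significant in 27%, against 82% detection between arms. A stricter threshold does not change what the paired test measures.

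**7. Sensitivity to the shared improvement** (active +0.5 SD at 6 months, r = .5, given a significant interaction):

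| Shared improvement (SD) | 0 | 0.1 | 0.2 | 0.3 | 0.4 | 0.5 |
|---|---|---|---|---|---|---|
| Baseline to 3 months: exactly one arm significant | 11% | 22% | 46% | 49% | 25% | 7% |
| Baseline to 6 months: both arms significant | 4% | 7% | 25% | 56% | 83% | 96% |

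The between-arm test stays near 6% and 90% throughout. At shared 0.3 SD, with r = .3 or .7, the exactly-one-arm figure is 54% or 27%, and the both-arms figure is 36% or 83%.

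**8. The missing estimate.** The 95% CI half-width for the between-arm difference in change is 1.98 x sqrt(2/60) = 0.36 SD.

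**The case against.** The strongest reply is that the SAP, read as a whole, does intend between-arm comparisons. Its power statement refers to tests of hypothesized differences between active and control. The Design paragraph allows interactions to be decomposed by a priori comparisons, and the group difference is the obvious candidate. This weakens any claim that the plan ignores the comparison, but it does not repair the step. The power statement names no time point or change score and is not tied to the follow-up, and the decomposition rule names no contrast. The only specific instruction is the paired t-test.

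Paired may also be a slip for pairwise. That is possible and the documents do not settle it. The sentence would still need correcting, since pairwise comparisons could run over times or over arms.

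It is fair to say that the main inference is untouched and that means by arm and time will be tabulated. The point difference can be derived from those means. An interval for the difference in change cannot be, without the SD of change or the correlation. The absence of confidence intervals is also general in the SAP and not peculiar to this sentence.

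Finally, the illustration depends on the shared improvement. With none, the paired pattern points to the right interval in most trials. Two significant within-arm results are also not errors in themselves when both arms truly change; they mislead only if read as showing no difference. These limits stand and bear on the size of the problem. They do not alter the fact that the named test cannot examine a treatment difference.

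**Conclusion.** The concern holds. As written, the SAP names a test that cannot serve its stated purpose, and it specifies no between-arm contrast or interval for that step. This follows from the design alone and needs no assumed numbers.

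The consequence is confined to locating and sizing an effect after a significant interaction. It does not inflate the overall false-positive rate. How often the paired tests would mislead depends on assumptions the documents do not supply: it is small when neither arm changes for reasons other than treatment. With shared improvement of 0.2 to 0.4 SD at r = .5, it runs from about a quarter to a half of gated trials at 3 months, and from a quarter to over four-fifths at 6 months. The point should be fixed, but it does not undermine the main test.

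**What to change.** Replace the follow-up sentence in the Analysis paragraph with wording such as: *Each significant interaction will be followed up with between-group contrasts (active minus control) in change from baseline at 3 months and at 6 months, estimated from the same model (or by independent-samples t-tests on change scores), with 95% confidence intervals; any within-arm paired t-tests are descriptive.*

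The cost is one sentence in the SAP. No new data are needed. Under the assumptions above (60 per arm, no dropout, r = .5, a true difference of 0.5 SD), each contrast has two-sided power of about .78 before conditioning on the interaction.

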Conversely, if only one or a very few measures reach statistical significance and their directions and/or magnitudes do not coherently fit with our a prior expectations, then we will note that the result(s) with  $p < 0.05$  lack plausibility and could be due to chance, despite meeting the conventional cutoff for statistical significance.

*Missing Data:* If subjects either cannot or refuse to complete surveys we will use a sensitivity analysis approach in dealing with these missing data by performing analysis with 2 versions of scores: 1) with missing item interpolated using mean replacement by group, and 2) only using responses with 0% missing data. If the results differ for the two approaches, then we will report on the differences.

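### Follow-up comparisons depend on significance, and no between-arm difference in change with a confidence interval is planned for any of the four outcomes

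*SAP*

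**What the plan says.** The SAP's Primary Outcomes section lists four scales (burden, depression, anxiety, life satisfaction) and defines the outcomes as changes over the 6-month study period.

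Under Statistical Methods, the Analysis paragraph fits a repeated measures ANOVA with a group-by-time interaction "to examine treatment group-related differences in the assessments for each outcome". It continues: "Each significant interaction will be followed up", and names paired t-tests as the method. The Design paragraph has a parallel rule: "significant main effects and interactions will be decomposed using a priori or post hoc comparisons depending on whether they are hypothesized or not". Both rules make follow-up depend on significance.

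The Analysis paragraph also plans summaries that do not depend on any test: "These will be summarized overall, by treatment group, by assessment time, and by treatment group and time". For continuous data, "Continuous variables will be summarized using means, standard deviations, and ranges". The sentence that introduces them is "Descriptive statistics will be used to summarize all the clinical characteristics and demographic outcomes", which does not name the four scales.

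The plan then forgoes formal adjustment across the four outcomes if the results form a coherent pattern. It treats one or a few significant measures as possibly due to chance if "their directions and/or magnitudes do not coherently fit with our a prior expectations". Neither document mentions a confidence interval.

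**The concern.** When the same data decide both whether a comparison is made and how large it looks, the estimates that survive are on average too large. An omnibus interaction F with 2 numerator degrees of freedom gives no direction and no difference at month 3 or month 6. The plan's only formal route to a time-specific comparison is therefore the significance-dependent one.

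Two things are at stake. Small to medium effects on burden, depression, anxiety or life satisfaction could be overstated where they are reported. Where the interaction is not significant, the reader would have no planned interval to show whether the result excludes a useful effect or is merely imprecise. The second point matters more here than in most trials, because the plan uses a judgement about the pattern over four outcomes instead of a multiplicity adjustment. That judgement needs a comparable estimate, with its precision, for all four.

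**Working it through.** **Inputs.** 60 caregivers per arm (protocol, Randomization); three assessments, r = .5 and alpha = .05 (SAP, Statistical Methods). Assumed, because the documents do not give them: SD 1 at each visit, equal correlations, no attrition, and a medium effect taken as Cohen's f = 0.25 or a difference of 0.5 SD.

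**1. The plan's own figure.** The SAP gives .99 power for the interaction. With λ = f²·N·m/(1 − r) = 0.0625 × 120 × 3 / 0.5 = 45 on 2 and 236 df, power is 0.99999. Without the (1 − r) divisor, λ = 22.5 and power is 0.992. Either is compatible with .99.

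**2. What that power means as a difference between arms.** Let d be the true between-arm difference in baseline-to-6-month change, in SD units. The noncentrality is λ = (n/2)·Σ(δₜ − δ̄)²/(1 − r), with n = 60.
- Linear divergence (0, d/2, d): Σ = d²/2, so λ = 30 × (d²/2)/0.5 = 30d².
- Equal effect at months 3 and 6 (0, d, d): Σ = 2d²/3, so λ = 30 × (2d²/3)/0.5 = 40d².

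At d = 0.5, λ is 7.5 or 10, and power is 0.68 or 0.81. Reaching λ = 22.5 needs d = √(22.5/30) = 0.87 or √(22.5/40) = 0.75. Reaching λ = 45 needs d = 1.22 or 1.06. So .99 power applies to differences in change well above 0.5 SD.

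**3. Effect of reporting only after a significant interaction.** Simulated 2 × 3 mixed ANOVA, at least 20,000 trials per case. The estimate is the between-arm difference in 6-month change.

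| True d (SD) | Linear: significant | Linear: mean if significant | Equal: significant | Equal: mean if significant |
|---|---|---|---|---|
| 0.2 | 15% | 0.44 (2.2×) | 19% | 0.40 (2.0×) |
| 0.3 | 29% | 0.50 (1.7×) | 38% | 0.45 (1.5×) |
| 0.5 | 68% | 0.59 (1.2×) | 81% | 0.55 (1.1×) |
| 0.8 | 98% | 0.81 (1.0×) | 99.7% | 0.80 (1.0×) |

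Averaged over all trials, significant or not, the estimate equals the true value in every case. With no true effect the interaction is significant 5% of the time, and the mean absolute estimate in those trials is 0.33 SD.

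**4. Precision of a difference in change.** The variance of a change score is 2(1 − r) = 1, so the standard error of the between-arm difference is √(2 × 1/60) = 0.183 and the 95% half-width is 1.96 × 0.183 = 0.36 SD. An observed difference of 0.20 SD would have an interval of about −0.16 to 0.56, which includes both zero and 0.5 SD.

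**5. Can the descriptive tables supply this?** Visit-specific SDs do not give r. With SD 1, the half-width 1.96·√(4(1 − r)/60) is 0.42 at r = .3, 0.36 at r = .5 and 0.28 at r = .7. The tables could give a crude difference in change, but not its interval.

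**The case against.** The strongest reply is that the plan already reports more than the follow-up rule suggests. Summaries by group and time carry no significance condition. The four scales are the only named outcomes measured at all three assessments, so the summaries very probably cover them. Arm means and SDs would then be available for every outcome, and differences, standardized effects and approximate intervals at a single visit could be derived. This largely stands. It does not supply the precision of the difference in change, which is how the SAP defines its outcomes.

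A reader might infer three stronger claims that the documents do not support:
- That effect sizes appear only where chance helped. The ungated summaries count against this, and at a true 0.8 SD selection adds almost nothing.
- That non-significant outcomes get no comparison at all. The interaction is tested for every outcome, and that is a between-arm comparison.
- That the coherence rule is applied only to a selected subset, or must use magnitudes for all four outcomes. The one explicit mention of directions and magnitudes concerns the measures that reach significance, and the rest of the rule refers only to the results in general.

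It can also be said that the inflation figures concern a quantity the plan does not promise: paired t-tests, taken literally, compare time points within persons. That is correct, so the figures are conditional. It also means that even a significant outcome might get no between-arm magnitude, which supports the remedy. Finally, the .99 power claim might suggest that the interaction test hardly selects at all. Step 2 of the working shows that this holds only for differences in change of roughly 0.75 SD or more.

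**Conclusion.** The point holds in a limited form. Time-specific follow-up depends on a significant interaction or main effect, and no active-minus-control difference with a confidence interval is planned for any outcome. If between-arm differences in 6-month change are reported only after a significant interaction, they are inflated by about 2.0-2.2 times at a true 0.2 SD, 1.5-1.7 times at 0.3 SD and 1.1-1.2 times at 0.5 SD; at 0.8 SD the inflation is negligible. Outcomes that are not significant would lack a stated precision, with a half-width of about 0.36 SD, while the plan relies on a pattern across all four.

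The sizes rest on 60 per arm, r = .5, SD 1, no attrition and the two effect patterns shown. The inflation is not a claim about what will be published: it applies only if the differences are reported selectively, and the descriptive tables may soften it. The absence of a planned interval does not depend on these assumptions.

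**What to change.** Amend both the Analysis and the Design paragraphs of Statistical Methods, since changing only one would leave the other rule in conflict with it. Suggested wording: *For all four outcomes, whatever the p-value of the interaction or main effects, the active-minus-control difference in change from baseline at months 3 and 6 will be reported with its 95% confidence interval. The judgement of coherence across outcomes will be based on these estimates. The Condition by Time interaction remains the formal test.*

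It would also help to name the four scales in the sentence on descriptive statistics. The cost is one extra table and small wording changes. No new data are needed, and error control is unaffected because the formal test does not change.
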